#### 5.1.2 Non-Hematological Toxicity

Patients who have Grade 3 or Grade 4 non-hematological toxicity attributable to the study drug prior to the Day 8 dose (with the exception of the DLT exclusions in [Section 5.2.1.1](#)) will be considered to have had a DLT. If the toxicity resolves to meet eligibility or  $\leq$  Grade 2 (if not part of eligibility criteria) by Day 8, the dose (along with dexamethasone support) may be given but at the next lower dose level. If the toxicity does not resolve by Day 11, the dose (along with dexamethasone support) will be omitted. Patients should receive subsequent cycles of drug but with dose modifications according to [Section 5.4](#).

Patients who require more than 2 dose reductions must be removed from protocol therapy.

All dose modifications should be based on the worst preceding toxicity.

### 5.2 Definition of Dose-Limiting Toxicity (DLT)

DLT will be defined as any of the following events that are at least possibly, probably or definitely attributable to IMG901. Dose-limiting hematological and non-hematological toxicities are defined differently.

### 5.2.1 Non-Hematological Dose-Limiting Toxicity

5.2.1.1 Any Grade 3 or higher non-hematological toxicity attributable to the investigational drug with the specific exclusion of:

- Grade 3 nausea and vomiting
- Grade 3 ALT/AST elevation that returns to Grade  $\leq 1$  or baseline prior to the time for the next treatment cycle. Note: For the purposes of this trial the ULN for ALT is defined as 45 U/L.
- Grade 3 fever or infection
- Grade 3 hypophosphatemia, hypokalemia, hypocalcemia and/or hypomagnesemia responsive to oral supplementation.
- Peripheral neuropathy Grade 3 for  $\leq 7$  days

5.2.1.2 Non-hematological toxicity that causes a delay of  $\geq 14$  days between treatment cycles.

5.2.1.3 Grade 2 allergic reactions that necessitate discontinuation of study drug will not be considered a dose-limiting toxicity.

### 5.2.2 Hematological Dose-Limiting Toxicity

5.2.2.1 Definition of a Hematological Dose-Limiting Toxicity for Patients without Bone Marrow Involvement at Enrollment

- Grade 3 thrombocytopenia occurring in conjunction with Grade 3 bleeding (CTCAE terms hemorrhage or epistaxis)
- Grade 4 neutropenia for  $> 7$  days
- Platelet count  $< 20,000/\mu\text{L}$  on 2 separate days, or requiring a platelet transfusion on 2 separate days, within a 7 day period
- Myelosuppression that causes a delay of  $\geq 14$  days between treatment cycles
- Any Grade 5 hematological toxicity.

## 5.3 **Dose Modifications for Hematological Toxicity**

5.3.1 Patients who have dose-limiting thrombocytopenia should receive subsequent cycles at the next lower dose level. Patients who require that their Day 8 dose be omitted for platelets  $< 75,000 \mu\text{L}$  after an initial dose reduction should have all future Day 8 doses omitted.

5.3.2 Patients who have dose-limiting neutropenia (Grade 4 neutropenia of  $> 7$  days duration or delay in the start of the next cycle for  $> 14$  days due to neutropenia) with no other dose-limiting toxicity should receive the same dose in the next cycle with myeloid growth factor support administered the next day after the Day 8 dose of IMGN901 is given. [Note: Patients MUST NOT receive prophylactic myeloid growth factor in the first cycle of therapy.] If dose-limiting neutropenia recurs after myeloid growth factor is added, then the patient should be given the next lower dose level followed by myeloid growth factor support beginning the next day after

the Day 8 dose of IMG901 is given for subsequent cycles. Patients who experience dose-limiting neutropenia after the addition of myeloid growth factor and one dose reduction must have all future Day 8 doses omitted.

- 5.3.3 Patients who experience dose-limiting hematological toxicity after a single dose reduction (and the addition of myeloid growth factor if the DLT is neutropenia) must have all future Day 8 doses omitted.
- 5.3.4 Patients who experience dose-limiting hematological toxicity in cycles after Day 8 doses were required to be omitted as above must be removed from protocol therapy.

#### 5.4 **Dose Modifications for Non-Hematological Toxicity**

- 5.4.1 Patients who have any dose-limiting non hematological toxicity (as defined in [Section 5.2.1](#)) that returns to eligibility lab requirements within 14 days after the planned start of the next treatment cycle may continue on study but should receive subsequent doses at the next lower dose level. Peripheral neuropathy must resolve to Grade 2 or lower following Grade 3 or 4 peripheral neuropathy prior to resumption of therapy, but it does not need to resolve to eligibility criteria.
- 5.4.2 If non-hematological dose-limiting toxicity recurs at the reduced dose, the patient must have all future Day 8 doses omitted.
- 5.4.3 Patients who experience dose-limiting non-hematological toxicity in cycles after Day 8 doses were required to be omitted as above must be removed from protocol therapy.

5.4.4 For patients who have allergic or acute infusional reactions to IMG901 therapy modifications based on grade should be as follows:

Infusion reactions and delayed infusion-related reactions	Any potential infusion reaction should be classified based upon severity and time of onset relative to the infusion and reported as an infusion reaction and the underlying symptoms on the AE CRF.	
	Mild or moderate (Grade 1-2)	
 
• Grade 1: Slow infusion rate by 50% and monitor patient for worsening of condition. Future infusions should be given at the 50% rate.
 
• Grade 2: Stop infusion; symptom control as per institutional guidelines (e.g., narcotics, IV fluids). Give diphenhydramine 0.5-1 mg/kg (max 50 mg IV) and may consider additional hydrocortisone 1-2 mg/kg (max 250 mg IV) or dexamethasone 4 mg/m^2 (max 10 mg IV or PO). Resume infusion at 50% of the prior rate once the reaction has decreased to ≤ Grade 1. Monitor patient for worsening condition. Discontinue IMG901 treatment if condition worsens. For subsequent doses, add diphenhydramine 0.5-1 mg/kg (max 50 mg IV) to the premedication regimen and infuse at 50% rate.
 

	Severe or life-threatening: (Grade 3-4)	
 
• Grade 3: Stop infusion immediately and disconnect the infusion tubing. Administer bronchodilators for bronchospasms, and other medications (e.g., epinephrine, Normal Saline) as medically indicated. Hospital admission should be considered. For subsequent doses, add diphenhydramine 0.5-1 mg/kg (max 50 mg IV) to the premedication regimen and infuse at 50% rate.
 
• Grade 4: Discontinue IMG901. Treat per institutional guidelines.
 

	*NOTE: Infusional reactions usually occur during or within 24 hours of the drug administration. If infusional reactions are suspected more than 24 hours after the dosing of IMG901, the patients should be treated as per institutional guidelines and the study chair should be notified.	

[REDACTED]

6.1.6

[REDACTED]

[REDACTED]

6.2

[REDACTED]

[REDACTED]

[REDACTED]

[REDACTED]

[REDACTED]

## 7.0 EVALUATIONS/MATERIAL AND DATA TO BE ACCESSIONED

Timing of protocol therapy administration, response assessment studies, and surgical interventions are based on schedules derived from the experimental design or on established standards of care. Minor unavoidable departures (up to 72 hours) from protocol directed therapy and/or disease evaluations (and up to 1 week for surgery) for valid clinical, patient and family logistical, or facility, procedure and/or anesthesia scheduling issues are acceptable per COG administrative Policy 5.14 (except where explicitly prohibited within the protocol). This policy does NOT apply to eligibility requirements; but to therapy and evaluations post consent and post the start of protocol directed care.

### 7.1 End of Therapy & Follow-up

STUDIES TO BE OBTAINED	End of Therapy
History	X
Physical exam with VS	X
Ht, Wt, BSA	X
Performance status	X
Pregnancy test	X
CBC, differential, platelets	X
Electrolytes including Ca ++ , PO 4 , Mg ++	X
Creatinine, SGPT, total bilirubin	X
Tumor disease evaluation	X

See COG Late Effects Guidelines for recommended post treatment follow-up:

<http://www.survivorshipguidelines.org/>

**Note:** Follow-up data must be submitted in accordance with the Case Report Forms (CRFs) schedule.

### 7.2 Correlative Biology Studies

#### 7.2.1 Pharmacokinetics

**Currently PK is optional for all patients.**

Pharmacokinetics was required for the first 6 patients enrolled at COG Consortium (Phase 1) sites.

#### 7.2.1.1 **Description of Studies and Assay**

Peripheral blood samples will be collected for the purpose of determining 1) IMGN901 conjugate, 2) total antibody which measures the concentration of both free huN901 antibody and conjugated antibody, 3) free DM1 maytansinoid, and 4) immunogenicity (ADA). Concentrations of IMGN901 conjugate, total antibody, and ADA will be measured using validated ELISA assays. Free DM1 maytansinoid will be measured using a validated LC/MS/MS assay.

#### 7.2.1.2 **Sample Collection and Schedule**

Peripheral blood samples for IMG901 conjugate, total antibody, and ADA measurements will be collected in red top vacutainer tubes. Blood samples for free DM1 maytansinoid will be collected in vacutainer tubes containing heparin (green top) or EDTA (lavender top) and chemical additives to maintain DM1 maytansinoid stability. All samples should be drawn from a site distant from the infusion. The exact time that the sample is drawn along with the exact time that the drug is administered is to be recorded on the Pharmacokinetic Transmittal form in Rave.

Peripheral blood samples will be collected at the following time points during Cycle 1:

- **Day 1:** Pretreatment, end of infusion, and 2 hrs, 6 hrs, 24 hrs, and 72-120 hrs after the end of the infusion.
- **Day 8:** Pretreatment, end of infusion, and 2 hrs and 6 hrs after the end of the infusion.

#### 7.2.1.3 Sample Processing

IMG901 conjugate, total antibody, and ADA:

- a. Draw 3 mL of blood in red top or tiger top vacuum tube (no anticoagulant) at each indicated time point.
- b. Allow the tubes to remain at room temperature for 30 to 60 minutes to clot.
- c. Centrifuge tubes at 1500 RPM for 15 minutes at room temperature.
- d. Transfer serum to a separate tube and store in a -70°C freezer.

Free DM1 maytansinoid:

- a. Draw 3 mL of blood in chilled vacutainer tubes containing heparin (green top) or EDTA (lavender top) and chemical additives at each indicated time point.
- b. Invert tube 8-12 times and place in an ice water bath.
- c. Centrifuge at 2,000 rpm for 10 min in a refrigerated centrifuge set at 4°C.
- d. Following centrifugation, transfer plasma to a separate tube and store in a -70°C freezer (within 30 minutes of collection).

#### 7.2.1.4 Sample Shipping:

1. Day 1 and Day 8 PK samples should be batched, maintained at -70°C until shipment, and shipped together for each patient at the end of Cycle 1. Include a printed copy of the completed Pharmacokinetic Transmittal form (in Rave).
2. Place samples in a cryobox. Ensure the cryobox is closed and remains so in transit using shipping tape. Place the cryobox in a shipping container with sufficient dry ice to maintain samples at -20°C for at least 72 hours.
3. Each shipment should be prepared in accordance with IATA regulations.

4. Frozen samples should be shipped via **overnight FedEx, Monday through Wednesday. No shipments should be made later than Wednesday of any given week.**
5. **On the day of shipment:** Email a copy of the completed Pharmacokinetic Transmittal form (in Rave) and the tracking number to **[name]** ([contact]) and copy the **ADV1522 COG Study Assigned Research Coordinator** on the email.
6. Ship the PK samples to the following address

Attention: **[name]**  
Department of Oncology  
Mayo Clinic  
[name]  
[name]  
[name].  
[contact]  
[contact]  
Email: [contact]

#### 7.2.2 Peripheral Blood Cells CD56

**Peripheral blood cells CD56 count analyses will be performed for all patients participating in the optional pharmacokinetic studies.**

##### 7.2.2.1 **Summary of CD56 absolute count in whole blood:**

CD56-positive cells in peripheral blood will be measured using a MiltenyiMACSQuant 10 flow cytometer (MiltenyiBiotec) and a lyse-no-wash staining technique. The MACSQuant Instrument employs a volumetric sample uptake system, which allows for direct determination of an absolute cell count of the sample. Fifty microliters ( $\mu\text{L}$ ) of EDTA blood will be labeled with 10  $\mu\text{L}$  of anti-CD56 APC and 15  $\mu\text{L}$  of anti-CD45 FITC antibodies (BD Biosciences). The addition of CD45, a pan-leukocyte marker, allows for separation of debris and red blood cells from the leukocytes, and makes gating on the lymphocyte population more accurate. The blood is incubated with the antibodies and lysed with 925  $\mu\text{L}$  of FACSLyse red blood cell lysis solution. The sample is then analyzed on the MACSQuant flow cytometer using a program that yields both the percent of CD56-positive cells and the absolute number of positive cells per milliliter and per microliter.

##### 7.2.2.2 **Sample collection and Schedule:**

Peripheral blood samples are collected in an EDTA tube on Day 1 and Day 8 of Cycle 1 prior to (within 12 hours of starting) IMG901 administration. Minimum volume 1 mL. All samples should be drawn from a site distant from the infusion.

### 7.2.2.3 Sample Shipping

- a. Ship whole blood at room temperature along with a printed copy of completed Study Specimen Transmittal-Peripheral Blood CD56 form (in Rave). Note that extreme temperatures (hot or cold) can adversely affect shipped blood specimens. In winter when shipping temperatures can be far below freezing, it is best to ship with a warm pack or room-temperature cold packs in a well-insulated, double box (Styrofoam interior box/cardboard exterior box).
- b. Specimens may be shipped **Monday through Thursday** to be received Tuesday through Friday.  
Ship using FedEx First Overnight delivery. Specimen must be received in the laboratory within 24 hours of collection. We cannot accept deliveries on Saturdays or Sundays.
- c. **Shipping address**  

### 7.2.3 Tumor CD56 Expression (required)

CD56 expression will be assessed using standard immunohistochemistry. CD56 antibody, clone 123C3 from Ventana will be used. The procedure will be a fully automated immunohistochemical staining, performed at a Ventana Benchmark Ultra staining system and following a protocol clinically validated at Lurie Children's Hospital (Chicago).

Tumor cells will be recorded as either negative or positive. Only membranous expression will be considered. Positive staining will be interpreted qualitatively as the presence of coarse granular staining of the cell membrane in a circumferential pattern.

Scoring: 0-3+ according to percentage of positive cells (as defined above)

0-10% positive cells: 0

10-25% positive cells: 1+

25-50% positive cells: 2+

> 50% positive cells: 3+

Controls:

- 3+ blastemal Wilms tumor as positive control
- Patient's tumor sample not treated with CD56 antibody as negative control.

- 7.2.3.1 **Sample Collection**  
5 unstained slides of pre-treated tumor should be prepared on positively charged (“plus”) slides for immunohistochemistry.
- 7.2.3.2 **Sample Shipping**  
Slides should be shipped by regular mail in protective slide mailers along with a printed copy of the completed Specimen Transmittal-Unstained Tumor CD56 form (in Rave).
- 7.2.3.3 **Shipping address**  
See the Correlative Studies Shipment sheet on the ADVL1522 protocol web page for shipping account numbers.
- Ship Slides to:**  
[name]  
Department of Pathology  
Ann and Robert H Lurie Children’s Hospital of Chicago  
[name]  
[name]
- 7.2.3.4 **Contact**  
Please contact [name] at [contact] or email [[contact]](mailto:[contact]) for questions.

### 7.3 **Central Review**

The pertinent imaging studies (CT, MRI—and MIBG for neuroblastoma patients with I-MIBG positive lesions at start of therapy) of those patients who respond to therapy or have long term stable disease on protocol therapy will be centrally reviewed. COG Operations Center will notify the Imaging Research Center of any patient requiring central review. The Imaging Research Center will then request that the treating institution forward the requested images for central review. The central image evaluation results will be entered into Rave for review by the COG Operations Center and for data analysis.

The images are to be forwarded electronically to the Imaging Research Center at Children’s Hospital Los Angeles via the ImageInBox.

COG institutions that are not connected to the Imaging Research Center via the ImageInBox can send the images on CD ROM, DVD or USB flash drive for central review. Submitted imaging studies should be clearly marked with the COG patient ID, study number (ADV L1522) and date, and shipped to [name] at the address below:

[name], CCRP  
Administrator, Imaging Research Center  
Children’s Hospital Los Angeles  
[name]  
[name]  
[contact]  
[contact]  
Email: [[contact]](mailto:[contact])

## 8.0 CRITERIA FOR REMOVAL FROM PROTOCOL THERAPY AND OFF STUDY CRITERIA

### 8.1 Criteria for Removal from Protocol Therapy

- a) Relapse/progressive disease.
- b) Adverse Events requiring removal from protocol therapy, as stated in [Section 5.0](#).
- c) Patients who receive concurrent anticancer or investigational therapy, as stated in [Section 4.1.5](#).
- d) Refusal of further protocol therapy by patient/parent/guardian.
- e) Completion of planned protocol therapy.
- f) Physician determines it is in patient's best interest.
- g) Repeat eligibility studies (if required) are outside the parameters required for eligibility.
- h) Non-compliance that in the opinion of the investigator does not allow for ongoing participation.
- i) Patients who develop a second malignant neoplasm.
- j) Pregnancy.
- k) Breastfeeding.

Patients who are removed from protocol therapy (except for 8.1.g) are to be followed until they meet the criteria for Off Study (see below). Follow-up data will be required unless patient is taken off study.

### 8.2 Off Study Criteria

- a) Death.
- b) Lost to follow-up.
- c) Entry into another COG study with tumor therapeutic intent (e.g., at recurrence).
- d) Patient did not receive protocol treatment after study enrollment.
- e) Withdrawal of consent for any further data submission.
- f) The fifth anniversary of study entry.

## 9.0 STATISTICAL CONSIDERATIONS

### 9.1 Sample Size and Study Duration

#### 9.1.1 Patient Accrual and Expected Duration of the Study:

Three disease strata have been identified for reporting upon completion of evaluation of the particular disease stratum ('primary disease groups'). These disease strata are: (1) Wilms; (2) rhabdomyosarcoma; and (3) neuroblastoma. The evaluation rule is described in [Section 9.2](#) below.

In addition to the three main strata, enrollment into each of the following tumor groups ('secondary strata'): (4) pleuropulmonary blastoma, (5) malignant peripheral nerve sheath tumor, and (6) synovial sarcoma; will be open to accrual.

When the evaluation of the three primary disease groups is complete, enrollment to the study will be terminated unless the DVL committee leadership indicates further enrollment on the secondary strata is warranted.

If two of the three primary disease strata (Wilms, rhabdomyosarcoma, and neuroblastoma) have met their accrual and one remains open, the Cancer Therapy Evaluation Program (CTEP) and the ADVL1522 Investigators will discuss the study timeline.

Based on the enrollment rates prior to activation of Amendment #1, the following entry rates for the various tumors under study can be expected:

Disease Group/Strata	Patients/Year
1) Wilms tumor	18
2) Rhabdomyosarcoma	14
3) Neuroblastoma	9

For Wilms: 10 patients enrolled prior to activation of Amendment #1. Accrual of an additional 6 patients is expected to take approximately 4 months.

For rhabdomyosarcoma: 8 patients enrolled prior to activation of Amendment #1. Accrual of an additional 8 patients is expected to take approximately 7 months.

For neuroblastoma: 5 patients enrolled prior to activation of Amendment #1. Accrual of an additional 11 patients is expected to take approximately 14.5 months.

Allowing for roughly a 15% rate of ineligible/inevaluable patients, each stratum could need to enroll up to 19 patients to allow for 16 evaluable patients.

The study will likely require 2 to 3 years for sufficient patient enrollments to evaluate IMG901 in the three primary disease groups. If activity is detected in any category, further trials in subcategories of that category may be conducted at the discretion of the Developmental Therapeutics Steering and study committees. A maximum of 114 patients is anticipated.

### 9.2 Definition of Recommended Phase 2 Dose (RP2D)/ Tolerable Dose

The initial MTD defined in the adult trial is 112 mg/m^2/dose, approximated herein as dose

level 1 at 110 mg/m^2/dose. If there are < 2 DLTs in the first 6 patients treated at dose level 1 during the first cycle of therapy, this will be considered the RP2D and all subsequent patients will be enrolled at this dose level. If the MTD has been exceeded at Dose Level 1 as noted from the first six patients enrolled ( $\geq 2$  DLTs at least possibly attributed to IMG901), then the subsequent patients will be treated at Dose Level -1. If there are < 2 DLTs in the first 6 patients treated at dose level -1, this will be considered the RP2D and all subsequent patients will be enrolled at this dose level. A dose level -2 has been included in the proposal for purposes of providing a dose for those patients potentially accrued at dose level -1 (in the event it becomes the RP2D) and then subsequently requiring a dose reduction due to toxicity.

**Delayed Toxicity Monitoring:** We will monitor all serious adverse events on an ongoing basis. Analyses will be incorporated to screen for excess delayed peripheral neuropathy specifically.

A patient will be considered for toxicity monitoring if the patient is eligible and one of the following occurs: (1) completes one cycle of protocol therapy; (2) dies on protocol therapy for a reason considered possibly, probably, or likely related to protocol therapy; or (3) is removed from protocol therapy because of an adverse experience possibly, probably, or likely related to one of the agents. A toxicity-evaluable patient will be considered in the analysis during the interval from study enrollment until protocol therapy is terminated or, a toxicity-event is observed, whichever occurs first. A toxicity-evaluable patient will be considered to have experienced an excessive toxicity event if: (1) the patient dies on protocol therapy for a reason considered possibly, probably, or likely related to protocol therapy; or (2) experiences a dose-limiting toxicity.

The analytic unit for monitoring for excessive toxicity will be the patient-cycle: Each cycle where an excessive toxicity event is observed or where the patient receives the agent and completes the full cycle of treatment will be considered in the analysis. If there is overwhelming evidence that the dose selected for this trial has a per-cycle-excessive peripheral neuropathy (Grade 3 or higher) probability of more than 1/3, such information will be presented to the DSMB and consideration will be given to modifying any defined RP2D to one dose level lower.

We will use a Bayesian rule to monitor for excessive peripheral neuropathy. We will assume a beta prior distribution with  $\alpha = 0.6$  and  $\beta = 1.2$ . At least once per month, we will calculate the posterior probability (given the data) that the probability of Grade 3 or higher peripheral neuropathy (“Excessive PN”) exceeds the 1/3 threshold:

$$P(p_{\text{Excessive PN}} > 1/3 | \text{Data}) = \int_{1/3}^1 \frac{\binom{n}{x} p^x (1-p)^{n-x} \frac{\Gamma(1.8)}{\Gamma(0.6)\Gamma(1.2)} p^{-0.4} (1-p)^{0.2}}{\int_0^1 \binom{n}{x} q^x (1-q)^{n-x} \frac{\Gamma(1.8)}{\Gamma(0.6)\Gamma(1.2)} q^{-0.4} (1-q)^{0.2} dq} dp$$

where n is the number of excessive-PN-evaluable cycles and x is the number of such cycles on which an excessive PN event is observed. If this posterior probability exceeds 80%, such information will be presented to the DSMB and consideration will be given to modifying any defined RP2D to one dose level lower. Examples of situations in which this rule will indicate excessive toxicity have been noted and are presented below:

Number of Excessive PN-Evaluable Cycles	Number of Cycles with Excessive PN Observed	$P(p_{\text{Excessive PN}} > 1/3 \mid \text{Data})$
5	3	0.848
10	5	0.834
15	7	0.837
20	9	0.843
25	11	0.852
30	13	0.860
35	15	0.869
40	17	0.876

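### Section 9.2 closes a patient's monitoring at any DLT but applies the Bayesian rule to Grade 3+ neuropathy only, so some later cycles at an unchanged dose may go uncounted

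*Combined protocol and SAP*

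**What the plan says.** The delayed-toxicity part of Section 9.2 states its purpose: "Analyses will be incorporated to screen for excess delayed peripheral neuropathy specifically". It follows each toxicity-evaluable patient from enrollment to the end of protocol therapy or until "a toxicity-event is observed, whichever occurs first". The next sentence defines an excessive toxicity event as a treatment-related death on therapy or a patient who "experiences a dose-limiting toxicity". Neither limb is limited to neuropathy.

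The unit of analysis is the patient-cycle: "Each cycle where an excessive toxicity event is observed or where the patient receives the agent and completes the full cycle of treatment" is to be considered. The Bayesian rule has its own event, Grade 3 or higher PN, and its own denominator: "where n is the number of excessive-PN-evaluable cycles and x is the number of such cycles on which an excessive PN event is observed". No separate definition of such a cycle is given. The prior is Beta(0.6, 1.2) and the threshold is 1/3 per cycle. The action is: "If this posterior probability exceeds 80%, such information will be presented to the DSMB", with a one-level reduction of the RP2D then considered.

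Treatment can go on after a DLT. Under Section 5.3.2 a patient with dose-limiting neutropenia and no other DLT "should receive the same dose in the next cycle with myeloid growth factor support". Sections 5.3.1 and 5.4.1 move dose-limiting thrombocytopenia and recovered non-hematological DLTs to the next lower level. Section 5.2.1.1 excludes Grade 3 neuropathy lasting 7 days or less from the DLT definition.

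**The concern.** The event that closes a patient's interval is not the event being monitored, and the mismatch runs both ways. A neutropenia DLT closes the interval but is not neuropathy. A short Grade 3 neuropathy counts as excessive PN but, not being a DLT, leaves the interval open.

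The first mismatch matters more. A screen for delayed neuropathy depends on later cycles, and therapy may run to 17. If a patient drops out of the count at an unrelated DLT while still receiving the dose under evaluation, the rule loses cycles it was set up to observe. Because the evaluable cycle is undefined, two statisticians could also compute different n and x for a rule that is run at least monthly and can send the dose to the monitoring board.

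**Working it through.** **1. The plan's own figures.** With a Beta(0.6, 1.2) prior, the posterior probability is P = 1 − F(1/3; 0.6 + x, 1.2 + n − x), where F is the beta distribution function.

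| x/n | Stated in 9.2 | Recomputed |
|---|---|---|
| 3/5 | 0.848 | 0.8479 |
| 5/10 | 0.834 | 0.8343 |
| 7/15 | 0.837 | 0.8366 |
| 9/20 | 0.843 | 0.8434 |
| 11/25 | 0.852 | 0.8516 |
| 13/30 | 0.860 | 0.8601 |
| 15/35 | 0.869 | 0.8684 |
| 17/40 | 0.876 | 0.8765 |

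The table reproduces to within 0.0006, and each x is the smallest that passes 0.80 at its n. The arithmetic is sound; the question is which cycles enter it.

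**2. The sections side by side**, on the literal reading of 9.2:

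| Event | Closes the interval? | Counts in x? | Later cycles |
|---|---|---|---|
| Grade 3+ PN that is a DLT | Yes | Yes | Next lower level, once recovered (5.4.1) |
| Grade 3 PN for 7 days or less | No | Yes | Not governed by the DLT rules |
| Isolated dose-limiting neutropenia | Yes | No | Same dose with growth factor (5.3.2) |
| Dose-limiting thrombocytopenia | Yes | No | Next lower level (5.3.1) |
| Other recovered non-hematological DLT | Yes | No | Next lower level (5.4.1) |

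Illustration: a patient has isolated dose-limiting neutropenia in cycle 2, stays at the same dose, and has Grade 3 neuropathy in cycle 5. With the cut-off at any DLT, the patient contributes n = 2, x = 0. With the cycle sentence read alone, the patient contributes n = 5, x = 1.

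**3. Can the choice change the decision?** The documents give no counts of post-DLT cycles, so these are assumed. Take 15 counted cycles with 6 PN events: P = 0.680, no trigger. Add 5 same-dose post-DLT cycles with y PN events:

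| y | 0 | 1 | 2 | 3 | 4 | 5 |
|---|---|---|---|---|---|---|
| P | 0.358 | 0.541 | 0.712 | 0.843 | 0.927 | 0.971 |

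The rule triggers from y = 3. With y = 0, 1 or 2 it does not, and for y = 0 or 1 P falls below 0.680.

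**4. Chance of crossing at one look.** Take 30 counted cycles (boundary 13, since 12/30 gives 0.761) against 30 + 10 cycles (boundary 17, since 16/40 gives 0.798). Compare P(X ≥ 13) with P(X + Y ≥ 17), where X ~ Bin(30, p1) and Y ~ Bin(10, p2). All rates are assumed.

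| p1 (counted) | p2 (dropped) | Without the 10 | With the 10 |
|---|---|---|---|
| 0.30 | 0.10 | 0.08 | 0.01 |
| 0.30 | 0.30 | 0.08 | 0.06 |
| 0.30 | 0.50 | 0.08 | 0.20 |
| 0.30 | 0.60 | 0.08 | 0.30 |
| 0.35 | 0.60 | 0.22 | 0.50 |

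The direction depends on the PN rate in the dropped cycles.

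**5. Effect on the pooled rate if risk rises with exposure.** Assume PN risk p(k) rises linearly from 2% to 20% over 8 cycles, 20% of patients leave per cycle for other reasons, and a non-PN DLT with risk h per cycle ends counting. Then S(1) = 1, S(k+1) = S(k) × 0.80 × (1 − h) × (1 − p(k)), and the pooled rate is ΣS(k)p(k) / ΣS(k).

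| h | 0 | 2% | 5% | 10% |
|---|---|---|---|---|
| Pooled rate | 7.2% | 7.0% | 6.7% | 6.3% |

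There is a downward shift, but it is small, and none of these rates is near 1/3.

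**The case against.** The strongest reply is that 9.2 can be read without the defect. The cut-off speaks of a toxicity event for a toxicity-evaluable patient. The Bayesian rule uses a different unit and its own PN event, and the cycle sentence admits any cycle in which the agent is received and the cycle completed. This reading is possible, but nothing in 9.2 lifts the patient-level cut-off, and the only event defined beside it is a related death or any DLT. The ambiguity therefore stands as a defect.

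Three further replies limit the point, and they stand:

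- Most non-PN DLTs lead to a lower dose. Leaving those cycles out of a rule about the selected dose is defensible. The same-dose route is isolated dose-limiting neutropenia.
- That route may be rare. The DLT lists for the three single-agent adult studies in Section 2.3.1 name no hematological DLT; the patients with any DLT number 5 + 6 + 5 = 16 of 198 (8%). Adult DLT definitions may differ, so this is only a guide.
- Later neuropathy is not hidden. Ongoing SAE review (9.2), toxicity tables by worst grade per cycle (9.4), routine reporting of Grade 3+ events (11.12) and DSMC review (12.2) all remain, and the Bayesian trigger is advisory.

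A reader might go further and measure the loss as the share of patients already cut off before cycle k, 1 − (1 − h)^(k−1). With an assumed non-PN DLT risk of 5% per cycle that is 14% before cycle 4; with 10% it is 52% before cycle 8. These are shares of patients censored. They measure neither lost PN events nor bias, because cycles leave n as well as x.

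**Conclusion.** The point holds as a defect of definition with a limited consequence. On its plain text, 9.2 removes some later cycles at an unchanged dose from a monitor meant for delayed neuropathy, and it leaves the rule's counting unit undefined.

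The size cannot be obtained from the documents and may be small. If PN risk per cycle is constant and unrelated to other DLTs, there is no bias. The rate is understated only if risk is higher in the dropped cycles, as it would be if neuropathy were cumulative. The background makes that worth guarding against without establishing it: Section 2.3.1 reports late-occurring toxicities that lowered the expansion dose in one combination study, and Grade 3 neuropathy in 36% of patients at 112 mg/m² in another. Against this, single-agent Grade 3 neuropathy was 3%. All are per-patient figures or descriptions, not per-cycle rates. The cases in the working where the decision is likelier to change assume PN in 50% to 60% of the dropped cycles, which no figure in the documents supports.

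A reader might also infer that the patients removed are those most sensitive to the drug, so that the estimate must be low. DLTs are by definition attributed to the drug, but the documents give no data linking neutropenia to later neuropathy, so that inference is not supported.

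**What to change.** In 9.2, reconcile the follow-up sentence with the Bayesian rule:

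- Define an excessive-PN-evaluable cycle as one in which IMGN901 was given at the dose level under evaluation and the patient either completed the cycle or had Grade 3 or higher PN during it.
- End a patient's contribution to the PN rule at the first Grade 3+ PN event, whatever its duration, or at the end of protocol therapy. State that a non-PN DLT does not end it.
- Apply the rule to cycles at the dose under evaluation and tabulate reduced-dose cycles separately, so that they do not dilute the estimate.

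The cost is a sentence or two in 9.2 and a small change to a calculation already run at least monthly. Grade 3+ events are already collected (11.12). The prior, threshold and boundary table stay as they are, and no dosing rule is touched.
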